10.4 Performance Status

Patients will be graded according to the Zubrod Performance Status Scale.

POINT DESCRIPTION

- 0 Fully active, able to carry on all pre-disease performance without restriction.
- 1 Restricted in physically strenuous activity but ambulatory and able to carry out work of a light or sedentary nature, e.g., light housework, office work.
- 2 Ambulatory and capable of self-care but unable to carry out any work activities; up and about more than 50% of waking hours.
- 3 Capable of limited self-care, confined to bed or chair more than 50% of waking hours.
- 4 Completely disabled; cannot carry on any self-care; totally confined to bed or chair.

10.5 Progression-Free Survival

From date of registration to date of first documentation of progression (see note in Section 10.2d), or death due to any cause. Patients last known to be alive without report of progression are censored at date of last contact.

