7.6 Follow-Up Period

All patients will be followed, as indicated in Section 9.0, until 5 years after registration or death, whichever occurs first. Subsequently, patients will be asked to provide contact information for survival status follow-up (via phone) until 10 years after registration, for compliance with NIH OSP guidelines for long-term follow-up.

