8.5 Adverse Event Reporting

Toxicities (including suspected reactions) that meet the expedited reporting criteria as outlined in Section 16.0 of the protocol must be reported to the Operations Office, Study Chair and NCI via CTEP-AERS, and to the IRB per local IRB requirements.

S1607 Page 58 Version Date 10/15/2021

STUDY CALENDAR	
	UDY CALENDA

9.0

	Post- Prog Off Treat											[
												-
	Pre- Prog Off Treat		×									
	At Prog		×			×		×				
86 f	18 18											
Cycle 6-36 ^f	17 17											
Cyc	16 16									×	×	
	15 K											
Cycle 5	84 14											
O	13 K		×⊲							×	×	
	12 2 ≤											
Cycle 4	×1											
	10 10							×		×	×	
3	≷o		×									ļ
Cycle 3	⊗ ⊗											
	\geq \sim									×	×	
2	0 ≦											
Cycle 2	5											
	≥4					×		×		×	×	
-	s ⊗											
Cycle 1	2 🔨							×				
0	> -									×	×	
_	Pre- Study		Х			Х	х	×				
		X-RAYS AND SCANS	Tumor Measurements (CT/MRI) ^d		SPECIMENS	Tissue biopsy ^e	Archival tissue ⁱ	Blood Specimen Submission (20 ml) ^e	TREATMENT	Talimogene laherparepvec (T-VEC)	Pembrolizumab (MK- 3475)	Click here for Footnotes.

NOTE: Forms are found on the protocol abstract page on the SWOG website (www.swog.org). Forms submission guidelines are found in Section 14.0.

outlined in NOTE: Unless indicated otherwise in the protocol, scheduled procedures and assessments (treatment administration, toxicity as sessment for continuous treatment, disease assessment, specimen collection, and follow-up activities) must follow the established SWOG guidelines as https://www.swog.org/sites/default/files/docs/2017-10/Best%20Practices%20upddate.pdf.

S1607 Page 59 Version Date 10/15/2021

Partial Control Con	
 FOOTN A Disection A Dise	

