10.0 CRITERIA FOR EVALUATION AND ENDPOINT ANALYSIS

- 10.1 Measurability of Lesions
 - a. Measurable disease: Measurable disease is defined differently for lymph nodes compared with other disease and will be addressed in a separate section below.
 - Lesions that can be accurately measured in at least one dimension (longest diameter to be recorded) as ≥ 2.0 cm by chest x-ray, by ≥ 1.0 cm with CT or MRI scans, or ≥ 1.0 cm with calipers by clinical exam. All tumor measurements must be recorded in decimal fractions of centimeters (or millimeters).

The defined measurability of lesions on CT scan is based on the assumption that CT slice thickness is 0.5 cm or less. If CT scans have slice thickness greater than 0.5 cm, the minimum size for a measurable lesion should be twice the slice thickness.

- 2. Malignant lymph nodes are to be considered pathologically enlarged and measurable if it measures ≥ 1.5 cm in **SHORT AXIS** (greatest diameter perpendicular to the long axis of the lymph node) when assessed by scan (CT scan slice recommended being no greater than 0.5 cm).
- b. Non-measurable disease: All other lesions (or sites of disease), including small lesions (longest diameter < 1.0 cm or pathologic lymph nodes with ≥ 1.0 cm to < 1.5 cm short axis), are considered non-measurable disease. Bone lesions, leptomeningeal disease, ascites, pleural/pericardial effusions, lymphangitis cutis/pulmonitis, inflammatory breast disease, and abdominal masses (not followed by CT or MRI), are considered non-measurable as are previously radiated lesions that have not progressed

- c. Notes on measurability
 - 1. For CT and MRIs, the same type of scanner should be used and the image acquisition protocol should be followed as closely as possible to prior scans. Body scans should by performed with breath-hold scanning techniques, if possible.
 - 2. PET-CT: At present, the low dose or attenuation correction CT portion of a PET-CT is not always of optimal diagnostic CT quality for use with RECIST measurements. However, if the site can document that the CT performed as part of a PET-CT is of identical diagnostic quality to a diagnostic CT, then the CT portion of the PET-CT can be used for RECIST measurements and can be used interchangeably with conventional CT.
 - 3. Ultrasound: Ultrasound is not useful in assessment of lesion size and should not be used as a method of measurement.

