10.2 Objective Status at Each Disease Evaluation

Objective Status is to be recorded at each evaluation. All measurable lesions up to a maximum of 2 lesions per organ 5 lesions in total, representative of all involved organs, should be identified as target lesions at baseline. All other lesions (or sites of disease) including any measurable lesions over and above the 5 target lesions should be identified as non-target lesions. Measurements must be provided for target measurable lesions, while presence or absence must be noted for non-target measurable and non-measurable disease.

For studies that use disease progression as an endpoint, whole body scanning at specific intervals is necessary to determine that progression is NOT present outside of the "target" areas. Therefore, in these studies it is not acceptable to image only the "target" areas of the body in follow-up scans. For study-specific imaging requirements, see the Study Calendar in Section 9.0.

- a. Complete Response (CR): Complete disappearance of all target and non-target lesions (with the exception of lymph nodes mentioned below). No new lesions. No disease related symptoms. Any lymph nodes (whether target or non-target) must have reduction in short axis to < 1.0 cm. All disease must be assessed using the same technique as baseline.
- b. **Partial Response (PR)**: Applies only to patients with at least one measurable lesion. Greater than or equal to 30% decrease under baseline of the sum of appropriate diameters of all target measurable lesions. No unequivocal progression of non-measurable disease. No new lesions. All target measurable lesions must be assessed using the same techniques as baseline.
- c. **Stable**: Does not qualify for CR, PR, Progression or Symptomatic Deterioration. All target measurable lesions must be assessed using the same techniques as baseline.
- d. **Progression**: One or more of the following must occur: 20% increase in the sum of appropriate diameters of target measurable lesions over smallest sum observed (over baseline if no decrease during therapy) using the same techniques as baseline, as well as an absolute increase of at least 0.5 cm. Unequivocal progression of non-measurable disease in the opinion of the treating physician (an explanation must be provided). Appearance of any new lesion/site. Death due to disease without prior documentation of progression and without symptomatic deterioration (see Section 10.2e).

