NOTE: Any initial documentation of progression at the Week 9 assessment (or earlier) must be confirmed by a second determination of progression at the Week 13 assessment. If the Week 13 assessment documents an absence of progression, the patient's disease is assumed not to have progressed. If the Week 13 assessment is inadequate and there are no subsequent assessments documenting absence of progression, the initial documentation of progression will be considered definitive. After the disease assessment at Week 13, the documentation of any of the criteria in the paragraph above will be counted as disease progression.

Notes regarding new lesions: FDG-PET imaging can complement regular scans in identifying new lesions according to the following algorithm.

1. Negative FDG-PET at baseline, with a positive FDG-PET at follow-up is a sign of progression based on a new lesion.

- 2. No FDG-PET at baseline and a positive FDG-PET at follow-up corresponding to a potential new site of disease must have a confirmation by anatomical assessment (e.g., CT, MRI, x-ray) as new site of disease to be considered progressive disease. In such a case, the date of progressive disease will be the date of the initial abnormal FDG-PET.
- e. **Symptomatic deterioration:** Global deterioration of health status requiring discontinuation of treatment without objective evidence of progression. Efforts should be made to obtain objective evidence of progression after discontinuation.
- f. **Assessment inadequate, objective status unknown.** Progression or symptomatic deterioration has not been documented, and one or more target measurable lesions have not been assessed or inconsistent assessment methods were used.
- g. Objective status notes:
 - 1. Non-measurable and non-target measurable disease do not affect Objective Status in determination of CR (must be absent--a patient who otherwise has a CR, but who has non-measurable or non-target measurable disease present or not assessed, will be classified as having a PR). However, non-measurable and non-target lesions are included in determination of progression (if new sites of disease develop or if unequivocal progression occurs in the opinion of the treating physician).
 - 2. An objective status of PR or stable cannot follow one of CR. Stable can follow PR only in the rare case that tumor increases too little to qualify as progression, but enough that a previously documented 30% decrease no longer holds.

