10.6 Time to Death

From date of registration to date of death due to any cause. Patients last known to be alive are censored at date of last contact.

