10.7 Durable Response Rate

Complete or partial response per RECIST 1.1 with no evidence of disease progression for at least 180 days from the initial documentation of CR/PR. Patients last known to have an objective response but who are lost to follow-up before 180 days will be considered to have inadequate disease assessments. Patients known to have an objective response who have an objective response at the following disease assessment will be considered to have continued objective response in the interim, regardless of duration between disease assessments.

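### PFS is censored at last contact rather than at last disease assessment, so PFS rates run high to the extent that assessments stop before progression and it is not promptly reported; a minor, cheaply fixed weakness in a secondary estimate

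*Combined protocol and SAP*

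**What the plan says.** Section 10.5 counts PFS from registration to first documented progression or death, and adds: "Patients last known to be alive without report of progression are censored at date of last contact". Section 10.6 has the same rule for survival: "Patients last known to be alive are censored at date of last contact".

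Neither 10.5 nor section 11 has a PFS rule for missed or stopped assessments. The note in 10.2d, which 10.5 cites, deals with an inadequate Week 13 assessment only after progression has been recorded by Week 9. It does not reach a patient with no recorded progression.

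Other passages bear on this:
- Section 10.2 says that, where progression is an endpoint, "whole body scanning at specific intervals is necessary to determine that progression is NOT present outside of the 'target' areas". Section 10.2f classes an evaluation as unknown when "Progression or symptomatic deterioration has not been documented, and one or more target measurable lesions have not been assessed".
- Section 10.7 bridges a gap for responders "who have an objective response at the following disease assessment will be considered to have continued objective response in the interim". Section 10.5 sets no such condition.
- Section 14.4f asks for a follow-up form every 6 months in year 1 and yearly to year 5. After that, under section 7.6, "patients will be asked to provide contact information for survival status follow-up (via phone) until 10 years after registration".
- Sections 11.1c and 11.2c plan median PFS and PFS rates at a fixed time, with 6 months as the example in Cohort A. Precision is given as 23.7 points (17 patients) and 19.6 points (25 patients).

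**The concern.** For death, last contact is the right censoring date, because a contact shows that the patient is alive. It does not by itself show that disease has not progressed, and the protocol's own text says interval imaging is needed for that.

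Suppose scans stop at month 3, progression follows unseen at month 4, and the patient is reached at month 12. Section 10.5 then counts that patient as progression-free for all 12 months. The error has one direction, upward, and a confidence interval does not show it. At stake are the fixed-time PFS rates and, less so, the median PFS of objective 1.2e.

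**Working it through.** **1. The plan's own precision.** The half-width is 1.96 × √(0.25/n). For n = 17 this is 23.77 points (stated 23.7); for n = 25 it is 19.60 (stated 19.6). Both reproduce.

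**2. A simple count.** Each patient with unseen progression who is still in contact at 6 months adds 1/17 = 5.9 points in Cohort A or 1/25 = 4.0 points in Cohort B.

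**3. Illustration by simulation.** The documents give no PFS median and no stopping rate, so every input is an assumption: exponential progression with median 4 months; scan-stopping independent of progression in 10, 20 or 30% of patients; median survival of 14 months after progression; contact ending at 24 to 60 months; 400,000 patients per scenario; Kaplan-Meier estimates. True PFS is 2^(−6/4) = 35.4% at 6 months and 2^(−12/4) = 12.5% at 12 months.

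Continuous assessment, with 10/20/30% stopping:

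| Later progression reported | Censoring date | 6-month PFS (%) | 12-month PFS (%) |
|---|---|---|---|
| None | last contact | 38.0 / 41.2 / 44.6 | 17.4 / 22.8 / 28.4 |
| None | last assessment | 37.4 / 40.0 / 42.8 | 16.0 / 20.2 / 24.8 |
| Half, mean lag 3 months | last contact | 37.4 / 39.7 / 42.3 | 15.6 / 19.0 / 22.7 |
| Half, mean lag 3 months | last assessment | 37.1 / 39.0 / 41.3 | 14.9 / 17.6 / 20.6 |
| All, mean lag 3 months | last contact | 36.8 / 38.3 / 40.2 | 13.9 / 15.2 / 16.7 |

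If all later progression is reported promptly, last-contact censoring shows no bias (35.3% and 12.5%).

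- 6-month shift at 20% stopping: 41.2 − 35.4 = 5.8 points (none reported) and 39.7 − 35.4 = 4.3 (half).
- 12-month shift at 20% stopping: 22.8 − 12.5 = 10.3 and 19.0 − 12.5 = 6.5 points. In trial-size runs the standard deviation of the 12-month estimate was about 10 points (n = 17) and 8 points (n = 25).
- Share of the 12-month excess removed by last-assessment censoring at 20%: (22.8 − 20.2)/(22.8 − 12.5) = 25% (none); (19.0 − 17.6)/(19.0 − 12.5) = 22% (half); about 4% (all, lagged).

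The share is small because deaths after scans stop still count as events at their late dates, while living patients leave the risk set early.

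**4. Treatment of deaths.** Assume scans at weeks 9 and 13, then every 12 weeks, with 20% stopping at random. Full scanning gives 37.0% at 6 months and 14.2% at 12.

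| Rule | None reported: 6 / 12 months (%) | Half reported late: 6 / 12 months (%) |
|---|---|---|
| Last contact | 43.2 / 24.1 | 41.4 / 20.1 |
| Last assessment | 41.9 / 21.5 | 40.7 / 18.6 |
| Last assessment, and deaths after two or more missed scans censored | 36.9 / 13.8 | 38.1 / 14.8 |

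The third rule nearly restores the full-scanning value when nothing is reported later. It corrects only partly when progression is reported late, because those events keep their late dates. If patients stop scanning at the moment of unrecorded progression, the third rule still gives 18.8% (none) or 17.1% (half) at 12 months against 14.2%. No censoring rule recovers the full-scanning value in that case.

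**5. Median.** With continuous assessment and none reported, the median moves from 4.0 to 4.20/4.49/4.90 months. On the scan schedule it stays at the week-25 scan under every rule, except with 30% stopping at unrecorded progression and no later reporting.

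**The case against.** The strongest reply is that exposure may be small. The calendar in section 9.0 marks tumor measurements for patients off treatment before progression. Section 7.6 has all patients followed under section 9.0 for 5 years or until death. Section 10.2e asks for efforts to obtain objective evidence after symptomatic deterioration, the most obvious route to informative stopping. Section 14.4e requires an assessment form and radiology reports within 14 days of progression. Some contacts can detect progression without a scan, since lesions measuring at least "1.0 cm with calipers by clinical exam" are measurable. The years 5 to 10 phone contacts add nothing material at 6 or 12 months.

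All of this stands, and it makes the rows with no later reporting an upper bound for random stopping. It narrows the problem but does not supply a rule for a patient whose assessments lapse. The calendar footnotes cannot be read in the text available, so the off-treatment scan interval cannot be checked.

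It is also fair that 10.7 defines a yes/no response and is not a censoring rule. It shows a contrast with 10.5, not a contradiction.

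Finally, last-assessment censoring alone does little. That is correct, and it is why the fix has a second part.

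**Conclusion.** The point holds as a conditional one. Section 10.5 carries the survival censoring date into PFS, and this biases fixed-time PFS rates upward, and median PFS to a lesser degree, if assessments stop before progression and progression is not promptly reported by another route. With everyone assessed to progression there is no bias.

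The size cannot be derived from the documents. The illustration of about 4 to 6 points at 6 months rests on an assumed 4-month median, 20% random stopping, and none or half of later progression reported. It is well inside 23.7 and 19.6 points. The larger 12-month shifts refer to a time the plan does not name.

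A reader might infer that reported PFS will be materially inflated, or that the trial's conclusion is at risk. The documents support neither. They do not show that scans stop early, and they plan off-treatment scans. PFS is a secondary, single-arm, untested estimate, and the criteria for further study in 11.1b and 11.2b name response, toxicity and overall survival. A reader might also infer that moving the censoring date restores correct PFS; the working shows that it does not. This is a minor, cheap improvement.

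**What to change.** - In 10.5, censor patients who are alive with no documented progression on the date of their last adequate disease assessment, or at registration if there is none. Keep last contact for overall survival in 10.6 and as a PFS sensitivity analysis.
- Prespecify a sensitivity analysis that also censors, at the last adequate assessment, patients who die after two or more missed scheduled assessments. State that it is unbiased only if missed scans are unrelated to progression, and that it corrects only partly when progression is reported late.
- Report how many patients stopped scans before progression, and how many of those had progression reported later. These counts show whether the problem arose.

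The cost is one sentence, one short analysis and two counts. Assessment data are already due within 14 days of each assessment (section 14.4c). The downside is slightly lower PFS estimates, more early censoring, and reliance on missed scans being unrelated to progression. The response decision does not change.

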10.6 Time to Death

From date of registration to date of death due to any cause. Patients last known to be alive are censored at date of last contact.

10.7 Durable Response Rate

Complete or partial response per RECIST 1.1 with no evidence of disease progression for at least 180 days from the initial documentation of CR/PR. Patients last known to have an objective response but who are lost to follow-up before 180 days will be considered to have inadequate disease assessments. Patients known to have an objective response who have an objective response at the following disease assessment will be considered to have continued objective response in the interim, regardless of duration between disease assessments.

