- If talimogene laherparepvec (T-VEC) has to be permanently discontinued for any reason other than a complete response, patient will be removed from further treatment with pembrolizumab (MK-3475) and will come off study.

Table 2: Treatment delays and discontinuation due to Specific AEsrelated to T-VEC				
Condition	Grade	Talimogene laherparepvec (T-VEC) modification		
Injection site reactions	Any grade	Volume of talimogene laherparepvec (T-VEC) injection may be adjusted and should be held based on the degree of local toxicities		
Active herpetic cutaneous or mucosal lesions, herpes labialis, or active dermatoses in the region of the injected tumors	Any grade	Mild: continue talimogene laherparepvec (T-VEC) lf requiring systemic acyclovir or similar anti-viral agents: Hold talimogene laherparepvec (T-VEC).		
• Serious herpetic events such as herpetic encephalitis, encephalomyelitis or disseminated herpetic infection	Any grade	Discontinue talimogene laherparepvec (T-VEC)		
 Any condition requiring corticosteroid dosing of >10 mg prednisone daily (or equivalent) and/or other immunosuppressive medication for related toxicities 	N/A	Hold talimogene laherparepvec (T- VEC) dosing until corticosteroid dose has decreased to <10 mg prednisone daily (or equivalent) and the other immunosuppressive medication has been stopped.		
Plasmacytoma	Any grade	Permanently discontinue talimogene laherparepvec (T-VEC)		
 Immune-mediated AEs (These may include pauci-immune glomerulonephritis, vasculitis, and pneumonitis, but may involve any organ system) 	Grade 2 or greater	Hold talimogene laherparepvec (T- VEC) (with the exception of vitiligo). If delay is > 12 weeks, discontinue talimogene laherparepvec (T-VEC)		
• Allergic reactions, or urticaria	Grade 2 or greater	Hold talimogene laherparepvec (T- VEC). If delay is > 12 weeks, permanently discontinue talimogene laherparepvec (T-VEC)		
Other talimogene laherparepvec (T-VEC) related grade 3+ AEs or intolerable grade 2 AEs (Except brief grade 3 fever, fatigue, pain, or nausea/vomiting responding to supportive care)		 Hold talimogene laherparepvec (T-VEC) until AE is grade 0-1. If delay is > 12 weeks, discontinue talimogene laherparepvec (T-VEC) If the AE was grade 4, decision to resume talimogene laherparepvec (T-VEC) upon recovery should be reviewed with the sponsor (CTEP) 		

c. Concomitant Medication/Supportive Care Guidelines for pembrolizumab (MK-3475).

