10.3 Best Response

This is calculated from the sequence of objective statuses. Best response should be documented for as long as the patient remains on protocol treatment.

- a. CR: Two or more consecutive objective statuses of CR a minimum of four weeks apart.
- b. PR: Two or more consecutive objective statuses of PR or better a minimum of four weeks apart but not qualifying as CR.
- c. Unconfirmed CR: One objective status of CR but not qualifying as CR or PR.
- d. Unconfirmed PR: One objective status of PR but not qualifying as CR, PR or unconfirmed CR.
- e. Stable/no response: At least one objective status of stable/no response documented at least 6 weeks after registration, but not qualifying as anything else above.
- f. Increasing disease: Objective status of progression within 13 weeks of registration, not qualifying as anything else above.
- g. Symptomatic deterioration: Objective status of symptomatic deterioration within 13 weeks of registration, not qualifying as anything else above.

Inadequate assessment, response unknown: Progression or symptomatic deterioration greater than 13 weeks after registration and no other response category applies.

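### Section 10.7 lets a responder who stops for symptomatic deterioration, or who starts non-protocol anticancer therapy, count as durable, and it leaves some early deaths unscored

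*Combined protocol and SAP*

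**What the plan says.** Durable response is the first secondary objective (Section 1.2a). Section 10.7 defines it as "Complete or partial response per RECIST 1.1 with no evidence of disease progression for at least 180 days from the initial documentation of CR/PR". Two further rules follow. Responders "lost to follow-up before 180 days will be considered to have inadequate disease assessments". Responders who also respond at their next assessment "will be considered to have continued objective response in the interim, regardless of duration between disease assessments".

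Section 10.2 fixes what counts as progression. A death counts only if it is "Death due to disease without prior documentation of progression and without symptomatic deterioration". Symptomatic deterioration is a separate status: "Global deterioration of health status requiring discontinuation of treatment without objective evidence of progression". Section 7.4b ends protocol treatment for either.

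In Section 10.3, symptomatic deterioration is a best-response category only as "Objective status of symptomatic deterioration within 13 weeks of registration, not qualifying as anything else above", so it cannot displace an earlier CR or PR. The same section says: "Best response should be documented for as long as the patient remains on protocol treatment". Section 10.7 does not carry that limit into the 180 days.

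A responder can leave protocol treatment without progressing in other ways too. Under Section 8.2b, if T-VEC is stopped permanently for a reason other than complete response, the "patient will be removed from further treatment with pembrolizumab (MK-3475) and will come off study". Section 7.3 removes from protocol treatment anyone who needs a prohibited anticancer therapy. Section 7.6 follows all patients to 5 years or death.

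**The concern.** A durable response should mean that the response to this regimen held for 180 days. Section 10.7 tests something narrower, the absence of documented progression. The protocol itself creates exits that are neither progression nor loss to follow-up, and in two of them the literal definition gives a favourable score.

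The reported rate would then be too high, and later drugs could be credited to T-VEC plus pembrolizumab. Durable response is also the outcome in the CD8 analysis of non-injected tumors (Sections 11.1c and 11.2c) and in the Cohort A mutational-load analysis (Section 18.2), so misclassification would carry into those tests. With few responders, one patient is visible in the result. Without a rule, such cases would be settled one by one with outcomes known.

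**Working it through.** **1. The plan's own figure.** Sections 11.1c and 11.2c give 95% precision for the durable response rate of 23.7% (17 eligible patients) and 19.6% (25 eligible patients). The half-width at the least favourable rate of 50% is 1.96 × √(0.25/n).
- n = 17: 23.77% (stated 23.7%, apparently truncated).
- n = 25: 19.60% (stated 19.6%).

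Both reproduce, so all eligible patients are already the planning denominator.

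**2. Each exit before day 180, for a patient with CR or PR.**

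| Event | Status under Section 10.2 | Score under Section 10.7 |
|---|---|---|
| Objective progression | Progression | Not durable |
| Disease death, no prior symptomatic deterioration | Progression (10.2d) | Not durable |
| Loss to follow-up | Not progression | Inadequate assessment; place in the denominator not stated |
| Symptomatic deterioration, alive and in follow-up at day 180, no later scan showing progression | Not progression (10.2e) | Literally durable |
| Non-protocol anticancer therapy, still responding at the next scan | Not progression | Literally durable; response bridged across the gap |
| Disease death after symptomatic deterioration | Not progression (10.2d) | No rule |
| Death from another cause | Not progression | No rule |

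The PFS definition in Section 10.5, by contrast, names death from any cause.

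**3. Size per patient.** 1/17 = 5.9 points in Cohort A; 1/25 = 4.0 points in Cohort B. At the design alternatives the expected number of responders is 0.25 × 17 = 4.25 and 0.30 × 25 = 7.5, so in Cohort A one patient is about a quarter of the responders.

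**4. Illustration.** The documents give no frequency for these exits. The starting counts below are assumptions, near the case in which every expected responder is scored durable. Intervals are exact 95%.

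| Reclassified | Cohort A | Cohort B |
|---|---|---|
| None | 4/17 = 23.5% (6.8 to 49.9) | 7/25 = 28.0% (12.1 to 49.4) |
| One | 3/17 = 17.6% (3.8 to 43.4) | 6/25 = 24.0% (9.4 to 45.1) |
| Two | 2/17 = 11.8% (1.5 to 36.4) | 5/25 = 20.0% (6.8 to 40.7) |

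**5. Primary endpoint.** The probability of a positive conclusion is the sum, over first-stage counts x that pass stage 1, of P(X₁ = x) × P(X₂ ≥ r − x), where r is the final number of responses required.
- Cohort A (9 + 8 patients, continue on at least 1, r = 2): 17.2% at a true ORR of 5%, 90.2% at 25%, as stated.
- Cohort B (16 + 9 patients, continue on at least 2, r = 5): 9.5% at 10%, 90.3% at 30%, stated as 10% and 90%.

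These rules use confirmed CR/PR only. Section 10.7 does not enter them.

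**The case against.** **Scans are expected after treatment stops.** Section 10.2e asks for efforts to obtain objective evidence of progression after discontinuation, and the Section 9.0 calendar appears to mark tumor measurements off treatment before progression. The calendar footnotes could not be read in the copy reviewed, so a more specific scan rule may exist. This makes an unscanned responder less likely, but it does not say how to score one. Treating such a patient as inadequately assessed is a natural reading, but Section 10.7 reserves that for patients lost to follow-up.

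**Section 10.3 limits best response to time on protocol treatment.** True, but that limit governs whether a CR or PR is recorded. The 180-day condition is separate and has no such limit. The bridging sentence does require response at the very next assessment, which narrows the new-therapy case without closing it.

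**Scoring new therapy as failure is one of several defensible strategies.** This stands. The defect is that no strategy is stated and the literal text gives the favourable one.

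**The shift is small against the planned precision.** Also true: 5.9 and 4.0 points against ±23.7 and ±19.6. The error is systematic in direction, however, and the interval does not allow for it.

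Three stronger readings are tempting, and the documents do not support them:
- A reader might infer that durability can be lost only through progression. Loss to follow-up has its own rule.
- A reader might infer that early deaths count as durable. Disease death without symptomatic deterioration is progression. The other deaths are better called unscored, since a patient who dies before day 180 cannot plainly show 180 progression-free days.
- A reader might take the pivotal T-VEC trial's 16% durable and 26% objective response (Section 2.1) and compute 1 − 16/26 = 38% as the share of responders who fail within 6 months. Section 3.2b shows that its durable response also required onset in the first 12 months, while onset ranged to 16.7 months. The figure also pools progressions, which Section 10.7 already scores. It does not measure the exits at issue.

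**Conclusion.** The point holds for two exits. As written, Section 10.7 can score as durable a responder who stopped for symptomatic deterioration without later documented progression, and one who started non-protocol anticancer therapy and still responds at the next scan. Both biases are upward. For death from other causes and for disease death after symptomatic deterioration, the finding is only that no rule exists; no direction of bias is claimed.

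The size is 5.9 points per patient in Cohort A and 4.0 in Cohort B. The total effect cannot be estimated from the documents. The conclusion assumes that follow-up under Section 7.6 continues for patients who leave treatment, including those taken off under Section 8.2b, so that they are not simply lost to follow-up.

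This is a secondary endpoint and the ORR decision rules are untouched. It should be corrected before the durable response rate is analysed, but it does not threaten the primary conclusion.

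**What to change.** Amend Section 10.7 in three ways.

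1. Define durable response as CR or PR with none of these within 180 days of first CR/PR: progression, symptomatic deterioration, death from any cause, or start of non-protocol anticancer therapy.
2. Limit the bridging sentence to intervals in which no non-protocol anticancer therapy was given.
3. State that all eligible patients (the 17 and 25 already used in Section 11) form the denominator, and that anyone not meeting the definition, including those lost to follow-up, is scored as not durable.

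The cost is one paragraph of wording. Sample size and stated precision do not change. The reported durable response rate may be slightly lower. Section 14.4 lists forms by name without their fields, so the sponsor should confirm that the existing forms capture the start date of non-protocol therapy.
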